5.3 Progression of Study: Part A to Part B Go/No Go decision

A steering committee review of initial data from Part A along with the above information will occur with a view to deciding whether to proceed to Part B of the study. Factors that will be reviewed to help make this decision will be:

- 1. Recruitment rate the recruitment rate in Part A will be reviewed by members of the steering committee and may lead to amendments to Part B study duration
- 2. Adherence to required readings ≤ 75%

The steering committee has the following core members: the Chief Investigator, the protocol project manager and a representative from the Experimental Cancer Medicine's Team. Ad hoc members can contribute on an agenda-driven basis and voluntary contribution from patients is welcomed. There will be a clinical representative from both Nephrology and Oncology.

A red/amber/green traffic light (stop/amend/continue) approach, as described in the literature²⁵, will be applied to the criteria used to determine whether to progress with Part B. Hence, if a progression criterion is not met and cannot be mitigated, data gathered during the study will be used to revise the study protocol. If this is required regulatory processes will be followed as per Section 10 - Study Governance.

5.4 Randomisation

Participants will be randomised using a simple randomisation technique using an internet-based randomisation service²⁶. A permuted block technique will be used to ensure equal numbers in both groups.

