5.2 Part B

If, following Part A, the process is found to be an acceptable form of monitoring to patients, the study will continue to Part B. This will evaluate the potential for earlier diagnosis of AKI with intensive home monitoring of kidney function (plus standard of care monitoring) compared with standard of care only. The decision of whether to proceed to this stage of the study is described in further detail below. Participants who have been recruited to Part A of the study can continue to Part B if they so wish (and will be randomised).

Part B will enrol 60 patients being treated for cancer with potentially nephrotoxic anti-cancer therapies, randomised to either the intensive monitoring (device) group or the standard of care monitoring group, in a 1:1 ratio. Participants in both groups will be asked to complete a quality of life questionnaire at baseline. Both groups will receive standard of care monitoring of kidney function. In addition, participants in the intensive monitoring group will upload their creatinine reading three times per week (Mon/Wed/Fri) for 6 weeks. As in Part A, participants in the intensive monitoring group will be required to access the app on their own compatible device and upload their readings over their own internet connection. In both study arms, in line with scheduled clinic appointments (weeks B1, B3 and B6), blood and urine will be collected for exploratory biomarker analysis, along with renal function and cystatin C. When a participant attends a clinic appointment, a creatinine reading will be taken (either by the study participant or by a member of the study team) using the device, for comparison with the laboratory reading of creatinine taken that day.

During Part B of the study, when a participant has submitted their creatinine reading they will receive a successful submission message on the app and may receive feedback based on their reading (this depends on feedback from Part A of the study, performance of the amended algorithm from Part A and development of the smart phone application). As with Part A, participants will be directed to their

parent medical team if there is concern over their reading. Creatinine readings and AKI alerts from the algorithm will also be reviewed by the Chief Investigator once a week and highlighted to the parent medical team if there are concerns.

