6. SELECTION OF STUDY POPULATION AND WITHDRAWAL CRITERIA

Participants for both Part A and Part B will be identified from the general oncology outpatient population, with an initial focus on the Head and Neck Outpatient clinics. Anecdotally, this group of patients are high risk for AKI due to the nature of the treatment (platinum-based therapies) and increased risk of severe dehydration due to treatments that affect swallowing. Patients who have taken part in Part A of the study can continue to Part B if they wish and will be randomised prior to their participation in Part B.

Inclusion criteria

- Provision of signed and dated, written informed consent prior to participation in the study.
- Aged at least 18 years
- Receiving treatment for cancer with potentially nephrotoxic anti-cancer therapies (according to the judgement of the CI)
- Individuals whose medical team consider to be medically stable and able enough to take part or designated carer who would be able to perform the tasks required.
- Willingness and ability to self-monitor creatinine using device at home or have a
 designated carer who would be able to perform the tasks required. Part A device will
 be the NovaBiomedical StatSensor®.
- Access to smart phone and willingness to use, without reimbursement of any potential additional costs incurred, their iOS/Android device for the collection and transmission of information.

Exclusion criteria

- Being an employee, or closely linked with an employee, of the device company
- Judgment by the Investigator that the individual should not participate if they are unlikely to comply with study procedures and requirements.

- WHO performance status > 2
- Pregnancy

If withdrawal from the study occurs, permission will be sought to use their existing study data as well as data which forms part of their routine clinical care for the remainder of the study period. This will not require any further participation from the subject for the purposes of the study.

Possible reasons for withdrawal:

- 1. Withdrawal of consent
- 2. Pregnancy
- Loss of capacity/ability to carry out study requirements as deemed by participants primary medical team

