1.3 Format and scale of the data

Approximately 20 creatinine readings per study participant captured in encrypted electronic form. Baseline data capture in paper workbook and consolidated into excel workbook

Participant feedback from paper-based questionnaires.

Approximately 72 participants to be recruited (30 will be randomised in to the non-device group therefore will not be sending in creatinine readings)

2. Data collection / generation

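### Part B randomisation balances only the number per arm; blocking within one kidney-risk stratum would be a cheap improvement for a mixed population with 30 per arm

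*Protocol*

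**What the plan says.** Section 5.2 sets the size: "Part B will enrol 60 patients being treated for cancer with potentially nephrotoxic anti-cancer therapies", allocated 1:1. The data management plan (appendix 14.5, item 1.3) agrees on the control arm: "30 will be randomised in to the non-device group".

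Section 5.4 is the whole randomisation plan and has two sentences. The first is "Participants will be randomised using a simple randomisation technique using an internet-based randomisation service". The second is "A permuted block technique will be used to ensure equal numbers in both groups". Neither names a stratification or minimisation factor, and no block size is given.

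Section 6 describes participants as "identified from the general oncology outpatient population, with an initial focus on the Head and Neck Outpatient clinics". On the head and neck group it says "Anecdotally, this group of patients are high risk for AKI due to the nature of the treatment (platinum-based therapies" and adds dehydration, from treatments that impair swallowing, as a second reason. Every participant must meet the criterion "Receiving treatment for cancer with potentially nephrotoxic anti-cancer therapies (according to the judgement of the CI", so nobody in the trial is free of drug-related kidney risk.

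The Part B primary outcomes in Table 2 are time to AKI detection, AKI severity and change in renal function. Section 9 names a t-test and a one-way ANOVA, and leaves room for other analyses where appropriate.

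**The concern.** The protocol holds a view about who is at higher kidney risk and uses it to decide where to recruit first. It does not use that view when it allocates patients. All three Part B primary outcomes are kidney outcomes and the arms have only 30 patients each. A chance excess of higher-risk patients in one arm would push all three outcomes in the same direction, and the reader would have to work out how much of an observed difference comes from case mix.

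Timing matters too. Covariate adjustment can be settled in a statistical analysis plan. Stratified allocation has to be in place before the first Part B patient is randomised, so the protocol is where it belongs.

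**Working it through.** **Inputs from the protocol.** 60 participants, 1:1, so 30 per arm (section 5.2). Creatinine SD 0.2 mg/dl and planned difference 1.2 − 0.9 = 0.3 mg/dl (section 9).

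**Inputs not in the protocol, taken as assumptions.** K, the number of high-risk patients among the 60. The creatinine contrast g between risk groups, 0.2 to 0.3 mg/dl. Block size 4, where blocks are simulated.

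The protocol gives no imbalance figure to reproduce.

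**Step 1: chance of a 20-point gap.** 20 points of 30 is 6 patients. If X of the K high-risk patients fall in one arm, X is hypergeometric (60, K, 30) and the gap is |2X − K|. P(gap ≥ 6):

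| High-risk share | K | Probability |
|---|---|---|
| 10% or 90% | 6 or 54 | 2% |
| 20% or 80% | 12 or 48 | 10% |
| 25% or 75% | 15 or 45 | 7% |
| 30% or 70% | 18 or 42 | 16% |
| one third or two thirds | 20 or 40 | 17% |
| 50% | 30 | 20% |

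The dip at 25% and 75% arises because an odd K allows only odd gaps, so the threshold there is in effect 7 patients.

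**Step 2: does unstratified blocking help?** In 8,000 simulated trials per K, with blocks of 4 and risk groups arriving in random order, the probability was 7.7% (K = 15), 16.6% (K = 20), 19.5% (K = 30) and 17.0% (K = 40). These are close to Step 1, so blocking on numbers alone gives almost no protection.

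**Step 3: two situations that do protect.** With blocks of 4 generated within the risk stratum, the gap was at most 2 patients in every run. With unstratified blocks of 4 and all high-risk patients enrolled first, it was also at most 2.

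**Step 4: effect on the creatinine comparison.** Shift in the arm difference = imbalance × g:

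- g = 0.2: 0.20 × 0.2 = 0.04 mg/dl
- g = 0.3: 0.20 × 0.3 = 0.06 mg/dl

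The SD in section 9 is given for head and neck treatment. A half-and-half mix adds between-group variance, so SD = √(0.2² + 0.25 g²) and SE = SD × √(2/30):

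- g = 0.2: SD = √0.05 = 0.224, SE = 0.058, shift/SE = 0.04/0.058 ≈ 0.7
- g = 0.3: SD = √0.0625 = 0.25, SE = 0.065, shift/SE = 0.06/0.065 ≈ 0.9

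Against the planned 0.3 mg/dl, the shift is 0.04/0.3 = 13% to 0.06/0.3 = 20%.

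**The case against.** The strongest reply is that nothing here is wrong. Unstratified permuted blocks are a valid 1:1 design, and the error rate of the test already allows for chance imbalance. That stands. A reader might infer that the Part B comparison is biased, but the documents do not support this.

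A reader might also infer that an imbalance could not be told apart from a monitoring effect, or that the risk factor goes unadjusted. Neither follows. Section 7 collects previous cancer treatments, AKI risk factors, concomitant medication and baseline kidney function, so an imbalance would be visible and could be adjusted for. Table 2 includes change over the study, which removes baseline differences in level. Section 9 names no covariate, but adjustment is commonly left to an analysis plan, and none is shown.

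Nor is platinum-treated head and neck cancer shown to be the strongest risk factor. Section 6 calls the observation anecdotal and ranks nothing, section 3.4 lists many other causes of AKI, and all participants receive potentially nephrotoxic therapy. The contrast between groups is therefore unknown. The assumed 0.2 to 0.3 mg/dl has no source in the protocol and is large, at 67% to 100% of the planned difference.

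The probability also depends on how recruitment unfolds. The initial focus on head and neck clinics may mean those patients enrol first, or make up nearly all of the sample. Either would shrink the problem (Steps 1 and 3). The protocol guarantees neither, and it fixes no block size.

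What survives is narrower: allocation ignores the one patient group that the protocol singles out as high risk when choosing where to recruit, and a later analysis plan cannot add stratification.

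**Conclusion.** The point holds as a cheap design improvement. It does not show an error in the plan. The chance of a 20-point or larger gap in the high-risk share is about 2% to 20%: highest when half the participants are high risk, about 2% when nine in ten are, and lower still if head and neck patients enrol first in short blocks.

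If the gap occurs and the risk groups differ by 0.2 to 0.3 mg/dl, the arm difference moves by 0.04 to 0.06 mg/dl, about 0.7 to 0.9 of a standard error. That costs precision and makes a small trial harder to read, but it leaves the comparison valid. The probabilities rest on an assumed case mix and the shift on an assumed contrast; the protocol gives neither.

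**What to change.** In section 5.4, before Part B opens, state that the permuted blocks are generated separately within one two-level factor known before randomisation and matching the risk rationale in section 6. Platinum-based treatment versus other is one example. It fits that rationale better than head and neck platinum versus all other, which would place platinum patients with other tumours in the lower-risk stratum. Keep to a single factor, so that the strata stay large enough for 60 participants. Carry the factor into the Part B comparisons, in section 9 or in the analysis plan.

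The cost is one extra field in the internet-based service already planned and one term in the analysis. An incomplete block in each stratum may leave the arms one or two patients apart. The steering committee review between Parts A and B (section 5.3) is a natural point at which to make the change.

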6. SELECTION OF STUDY POPULATION AND WITHDRAWAL CRITERIA

Participants for both Part A and Part B will be identified from the general oncology outpatient population, with an initial focus on the Head and Neck Outpatient clinics. Anecdotally, this group of patients are high risk for AKI due to the nature of the treatment (platinum-based therapies) and increased risk of severe dehydration due to treatments that affect swallowing. Patients who have taken part in Part A of the study can continue to Part B if they wish and will be randomised prior to their participation in Part B.

Inclusion criteria

- Provision of signed and dated, written informed consent prior to participation in the study.
- Aged at least 18 years
- Receiving treatment for cancer with potentially nephrotoxic anti-cancer therapies (according to the judgement of the CI)
- Individuals whose medical team consider to be medically stable and able enough to take part or designated carer who would be able to perform the tasks required.
- Willingness and ability to self-monitor creatinine using device at home or have a
 designated carer who would be able to perform the tasks required. Part A device will
 be the NovaBiomedical StatSensor®.
- Access to smart phone and willingness to use, without reimbursement of any potential additional costs incurred, their iOS/Android device for the collection and transmission of information.

Exclusion criteria

- Being an employee, or closely linked with an employee, of the device company
- Judgment by the Investigator that the individual should not participate if they are unlikely to comply with study procedures and requirements.

- WHO performance status > 2
- Pregnancy

If withdrawal from the study occurs, permission will be sought to use their existing study data as well as data which forms part of their routine clinical care for the remainder of the study period. This will not require any further participation from the subject for the purposes of the study.

Possible reasons for withdrawal:

- 1. Withdrawal of consent
- 2. Pregnancy
- Loss of capacity/ability to carry out study requirements as deemed by participants primary medical team

During pregnancy, physiological changes affect creatinine readings and therefore they would not be a true reflection of renal function. For this reason, negative pregnancy status will be confirmed for all women of child bearing age who are taking part in the study if this has not already been done by the parent medical team prior to commencement of anti-cancer treatment.

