3.9 Patient and public involvement

There were 17 individual interactions with people currently involved in early oncology trials within The Christie NHS Foundation Trust. These included patients, carers, and staff, and focussed mainly on gaining insight into the applicability of the research question, usability and practicality of the device, performing readings, and the information provided. Feedback gathered during these discussions has directly informed the protocol and processes described within.

Two focus groups have also been conducted. The first with 3 participants who have previously had cancer. The second, with 4 renal patients at various stages of their treatment journey, 2 of whom had also received a treatment for cancer that affected their kidney function. The project was unanimously felt to be worthwhile and many were surprised by the current limitations that reduced kidney function can have on peoples' cancer-treatment options. Both groups liked the idea of having some control over their results and having more responsibility over their own health. Participants from the renal focus group specifically embraced taking their own readings and thought that it would be motivating for taking ownership of their health overall. Both groups of participants questioned whether a study involving this sort of technology and smart phones/apps would exclude a section of the population who are not 'tech-literate' or able to perform the reading for various reasons such as dexterity problems. They queried whether a reading could be carried out by carers as, at certain timepoints, patients undergoing cancer treatments may be intensely fatigued or unable to carry out readings for other reasons. If a patient would like to participate in the study and has a carer they would like to perform the testing, they will be trained to take the readings as such. In addition to providing feedback on the practicality of the approach and information provided, they have since reviewed and approved the final information leaflets and videos accompanying this trial.

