10. STUDY GOVERNANCE

10.1 Regulatory and Ethical Considerations

Prior to study initiation, a favourable ethical opinion will be obtained from the NHS Health Research Authority. All research activity will be conducted in accordance with the International Standard of Good Clinical Practice. The study sponsor will be the University of Manchester and all research activity will be conducted in accordance with trust policies. This feasibility study will be registered with the International Standard Randomised Controlled Trial Number Registry.

Study participants need access to a smart phone device to be able to take part in the study. This could possibly exclude a population of patients who may want to take part in the study but do not have a smart phone, for whatever reason. If this is found to be an issue, an amendment to the inclusion criteria to provide smart devices to these participants will be considered, or other options for these people to submit their results, such as computers.

Some study participants may not be able to physically take readings and send in the results. For these participants a carer will be designated to take the reading and send in the result.

Study amendments will be submitted as directed by regulatory requirements.

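### Section 6 makes inability to carry out study tasks a reason to leave the study, which risks health-related loss of Part B outcome data that differs by arm

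*Protocol*

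**What the plan says.** Protocol Section 6 lists three possible reasons for withdrawal, with no distinction between arms: withdrawal of consent, pregnancy, and "Loss of capacity/ability to carry out study requirements as deemed by participants primary medical team". It describes no intermediate status in which a participant stops home testing but stays in the study. After withdrawal, "permission will be sought to use their existing study data as well as data which forms part of their routine clinical care" for the rest of the study period, and the protocol adds: "This will not require any further participation from the subject for the purposes of the study".

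The tasks differ by arm. Section 5.2 says that "participants in the intensive monitoring group will upload their creatinine reading three times per week (Mon/Wed/Fri) for 6 weeks". Table 4 also marks the phone call, usability questionnaire and participant interview as intensive-group only. Both arms have standard-of-care kidney monitoring, quality-of-life questionnaires and clinic visits at which "blood and urine will be collected for exploratory biomarker analysis, along with renal function and cystatin C".

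The protocol expects that some people will become unable to test. Section 3.9 reports the focus groups' point that "patients undergoing cancer treatments may be intensely fatigued or unable to carry out readings for other reasons", and offers training to a carer. Section 6 allows a designated carer at entry. Section 10.1 says of those who cannot physically take readings: "For these participants a carer will be designated to take the reading and send in the result". The participant booklet treats a missed reading as one to make up later.

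Table 2 gives the Part B primary outcome measures: time to AKI detection, AKI severity at detection, and overall change in renal function over the study period.

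**The concern.** One withdrawal criterion covers both arms but sets a higher bar in one of them. A device-arm participant can become unable to do 18 finger-prick readings with uploads while still able to attend clinic. A control has no comparable task to fail. The judgement lies with the primary medical team. No blinding of that team is described, and Section 5.2 has device readings of concern passed to it.

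Inability to test is unlikely to be random. Section 6 describes the initial recruitment group as at high risk of AKI, partly through severe dehydration, and people too ill to test plausibly include those whose creatinine is rising. If their outcomes are lost from one arm, that arm's end-of-study creatinine, AKI count and AKI severity look better without any effect of monitoring.

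Data permission is the weak link. It is sought after withdrawal and covers even data already collected. No analysis plan can recover data that the study has no permission to use, so this cannot be left to the SAP.

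**Working it through.** **Inputs from the protocol.** 60 participants randomised 1:1, so 30 per arm (Section 5.2). Creatinine SD 0.2 mg/dl and assumed effect 1.2 − 0.9 = 0.3 mg/dl (Section 9). Home readings: 3 per week × 6 weeks = 18 in the device arm, 0 in the control arm.

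**Assumptions, because the protocol gives no withdrawal rate.** k device-arm participants are withdrawn and their outcomes are lost; no controls are lost unless stated; there is no true effect. Withdrawal goes to the k sickest, where sickness has correlation ρ with final creatinine. The SD of 0.2 is used for the compared quantity, since no SD of change is given. There is no plan figure on this point to reproduce.

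**Shift in the mean.** With n per arm and the k sickest removed from the device arm,

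expected shift = −[k/(n − k)] × SD × ρ × m,

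where m is the expected mean of the k largest of n standard normal values. For n = 30 the three largest have expectations 2.043, 1.616 and 1.365, so m = 5.023/3 = 1.674.

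- k = 3, ρ = 1: −(3/27) × 0.2 × 1.674 = −0.037 mg/dl, which is 0.037/0.3 = 12% of the assumed effect.
- k = 3, ρ = 0.5: half of that, −0.019 mg/dl, or 6% of the assumed effect.

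**Type I error.** Simulated two-sample t-test, two-sided 5% (level assumed), 20,000 runs per row. Ranges run from ρ = 0.5 to ρ = 1:

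| Lost, device / control | Shift, mg/dl | Type I error |
|---|---|---|
| 0 / 0 | 0.000 | 5.0% |
| 3 / 0 | −0.018 to −0.037 | 6.5% to 12.7% |
| 6 / 0 | −0.033 to −0.068 | 9.7% to 28.1% |
| 6 / 2 | −0.021 to −0.042 | 7.2% to 17.3% |
| 3 / 3 | about 0 | 5.6% to 8.4% |
| 3 / 0, ρ = 0 | about 0 | 4.9% |

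A repeat of the 3 / 0 row with 100,000 runs gave 6.7% and 12.6%, so the figures are stable to a few tenths of a percentage point. In the 3 / 3 row there is no bias; the remaining excess arises because removing the highest values from both arms makes the estimated SD too small.

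Section 9 speaks of 30 participants for Part B without saying whether that is per arm. With 15 per arm, losing 3 from the device arm gives −0.033 to −0.065 mg/dl and 7.4% to 15.2%.

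**Direction by outcome.** Losing sick device-arm participants lowers that arm's mean creatinine and removes AKI cases, including severe ones, so those comparisons move towards home monitoring. For time to AKI detection, the same loss removes device-arm participants in whom AKI might have been detected early. That could work against home monitoring, so no single direction can be stated.

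**The case against.** A reader might infer that the rule removes mainly sick device-arm patients, that the permission request fails to rescue their data, and that the whole arm comparison is biased towards home monitoring. The documents do not support that reading.

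- The item is a possible reason, applies to both arms, and comes with no expected rate. Controls also have visits, samples and questionnaires that they could become unable to complete.
- Carer testing is the protocol's direct answer to the patient too unwell to test, and the booklet treats missed readings as routine. This should prevent some of these withdrawals. It is not complete: Section 3.9 offers it where the patient has a carer, and the withdrawal item makes no exception for carer testing.
- The permission request fails only for those who cannot respond to it. Someone physically unable or fatigued can still agree to the use of routine results, which need no further participation. Loss of mental capacity should be uncommon in people judged medically stable, or supported by a carer, with performance status 2 or better over about six weeks.
- The consent form is not among the pages shown, so advance permission may already exist. Analysis by randomised arm may be set out in a SAP that is not shown.
- The upper figures assume that exactly the highest-creatinine patients are lost, with all their data, and that no controls are lost.
- The direction does not carry over to time to AKI detection.

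These points narrow the concern and lower its likely size. They leave two things standing: the text does not separate stopping home readings from leaving the study, and it gives no route for a participant who can no longer give permission.

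**Conclusion.** The point holds as a risk, not as a demonstrated bias. The withdrawal item is tied to tasks that fall far more heavily on one arm, the protocol itself recognises that patients may become too fatigued to test, and retention of data depends on a later request. Part B outcome data could therefore be lost in a way that depends on both arm and health.

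If 3 of 30 device-arm participants were lost and no controls, the creatinine difference would shift in favour of home monitoring by about 0.02 mg/dl (ρ = 0.5, type I error about 6.5%) to 0.037 mg/dl (the three highest, about 12.5%). The bias is near zero if loss is equal between arms or unrelated to creatinine, and there is none where the outcomes are in fact retained. The number lost and the correlation are assumptions. The direction is favourable to the device arm for creatinine change and for AKI count or severity, and uncertain for time to AKI detection.

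**What to change.** In Section 6, replace this withdrawal item with a separate status, *stops home readings*, which does not end study participation. For these participants:

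- keep routine-care laboratory creatinine and AKI data to the end of the study period;
- take research blood and urine only where consent still holds;
- analyse them in the arm to which they were randomised;
- confirm that the initial consent already permits keeping collected data and using routine results if the participant later cannot continue, and add that permission if it does not.

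Keep withdrawal of consent as its own category, with its own data rule.

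This is a cheap improvement: it adds no visits or tests. The downside is a protocol amendment and possibly a consent-form amendment. The Part A to Part B review in Section 5.3 already anticipates protocol revision and is a natural time to make the change.
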